5.5 Subject Compliance Monitoring

Patients will be present for face-to-face visits injection of the study medication, which will ensure the medication is appropriately administered.

5.6 Prior and Concomitant Therapy

Patients with prior use of home or office-based destructive treatments for this wart(s) in the last 1 month with SA or cryotherapy, immunoadjuvant therapy for warts in the last 4 months (e.g. Candida) history of vitamin D injection of warts ever, high-dose vitamin D supplementation (>4000 IU daily or equivalent) in the preceding 3 months, or immunosuppressive medications or conditions as judged by the physician evaluating the patient at the baseline visit.

5.7 Packaging

Cholecalciferol (vitamin D3) in sesame oil 40,000 IU/mL injections will be prepared from a fresh 1.5 ml vial and the unused portion of the vial discarded. Controls will receive a similar clear and equally viscous solution of sesame oil packaged in the same appearing vials. Study drug and placebo are provided by Mayo Production Lab and dispensed by Research Pharmacy. 90 study drug vials and 90 placebo vials will be provided by Research Pharmacy.

5.8 Masking/Blinding of Study

The pharmacy will prepare a stock of vials of vitamin D3 and placebo at intervals when requested. At their subsequent visit, participants will receive the same vial containing the same unknown as they received at their prior visit.

5.9 Receiving, Storage, Dispensing and Return

Subjects presenting for enrollment will be randomized by the pharmacy to receive either placebo or vitamin D3 for their injection, procured from the pharmacy at the time of enrollment by prescription and prior to each future visit, and picked up by Department of Family Medicine research coordinators.

5.9.1 Receipt of Drug Supplies

Mayo Production Lab will ship the vitamin D3 and placebo to the Research Pharmacy and the Department of Family Medicine research coordinators will pick up prior to each study visit.

Upon receipt of the vitamin D3 and/or placebo, an inventory will be performed and a drug receipt log will be completed as appropriate for the Research Pharmacy.

5.9.2 Storage

Mayo Research Pharmacy will store the vitamin D3 and placebo.

5.9.3 Dispensing of Study Drug

Regular study drug reconciliation will be performed to document drug assigned, drug dispensed, drug returns, and drug remaining. This reconciliation will be logged on the drug reconciliation form, and signed and dated by the Research Pharmacy.

5.9.4 Return or Destruction of Study Drug

At the completion of the study, there will be a final reconciliation of drug shipped, drug dispensed, drug returns, and drug remaining. This reconciliation will be logged on the drug reconciliation form, signed and dated. Any discrepancies noted will be documented and investigated, prior to return or destruction of unused study drug. Drug destroyed on site will be documented in the study files.

6 Study Procedures

- 6.1 Screening Visit: At this visit once it has been determined if the subject qualifies for this study and they agree to participate, they will be randomly assigned by chance (like a coin toss) to receive either Vitamin D or placebo injections into the wart of their choice. Neither the subject nor the study team can choose which group they'll be assigned to; we will find out at the end of the study.
- 6.2 Baseline Visit 1: The wart will be examined, photographs taken for measurements, medications will be reviewed and the subject will complete an initial study questionnaire. The wart will be sprayed for a few seconds with ethyl chloride to reduce discomfort just prior to receiving the injection. Within a week following the visit, the subject will receive a brief survey via email to complete which asks about their symptoms and pain. Each week after, the subject will receive an additional survey asking about pain until they report for 2 weeks without pain.
- 6.3 Visit 2 and 3 (Week 4 and Week 8) Visits: The subject will receive an injection in the index wart if it is still present (subject may send photograph ahead of time to study coordinator to determine),. At the visit, photographs will be taken of all warts for measurements, medications reviewed and they will be asked to assess their pain. A week following the visit a survey will be sent via email which asks about their symptoms and pain. Each week after, the subject will receive an additional survey asking about pain until they report for 2 weeks without pain.
- 6.4 Visit 4 (Week 12): The subject will return to have the wart examined. Photographs will be taken of all warts for measurements and medications reviewed. If the subject still reports of pain, a survey will be sent to assess until they report for 2 weeks without pain.
- 6.5 Study Completion (Week 24): The subject will return to have the wart examined. Photographs will be taken of all warts for measurements and medications reviewed. Payment for their participation will be processed at this time.

Only one wart will receive injections, however up to 8 others may be photographed, measured, and observed for any changes during the study.

Photographs of the subjects wart will be added to their electronic medical record.

The subject will be informed which group they were in after the study is completed and analyzed. If they continue to have persistent warts, they will be referred back to their primary care provider for treatment and provided with education for treatments available over the counter.

Schedule of Events:

Time point	Screening Visit ¹	Baseline/ Visit 1 (+ 7 Days) ¹	Visit 2 (+/- 7 Days)	Visit 3 (+/- 7 Days)	Visit 4 (+/- 7 Days)	Study Completion (+/- 7 Days)
Week	0	0	4	8	12	24
Day	0	1	28	56	84	168
Informed consent	X					
Randomization	X					
Vit. D Study Questionnaire		X				
Inject study medication		X	X⁵	X⁵		
Vitamin D Study Visit Form		X	X	X		
Take photo of wart		X⁶	X⁶	X⁶	X	X
Concomitant Meds. ²		X	X	X	X	X
REDCap Side effects survey ³		X	X	X		
REDCap Pain survey ⁴		X	X	X	X	
Subject remuneration						X

1. Screening and Baseline visit could take place on same day if patient prefers
2. To ensure subject has not been using any other wart treatments
3. REDCap side effects survey will be emailed one week after each visit
4. REDCap pain survey will be emailed one week after the REDCap side effects survey for every week until subject reports for 2 weeks without pain
5. If the index wart is still present
6. Subject may take photo of index wart ahead of time to determine if injection is needed

7 Statistical Plan

7.1 Sample Size Determination

We can reasonably estimate an efficacy rate of up to 3 intralesional injections of vitamin D into recalcitrant warts as high as 90% for and as low as 40%. Given the study design of a dichotomous outcome as dependent variable of complete resolution of the wart(s) in the two groups to be compared – intervention and control - and an anticipated incidence of 5% spontaneous resolution of recalcitrant warts over the course of the 24 weeks of the study and an anticipated effect size of the intervention of 35% additional complete resolution based on the Abdel Kareem study with a Type I/II Error Rate alpha of 0.05 and power of 80%, we would need a sample size of 54 composed of 27 subjects receiving the intervention and 27 controls. We will increase enrollment to 30 in each group to account for drop outs. Since Abdel Kareem enrolled pediatric patients age 12 and older who tend to have a higher spontaneous resolution of warts than adults, we can reasonably base our sample size calculation on his study. If a high percentage of the patients we enroll have non-recalcitrant and non-plantar warts, we can assume a higher

spontaneous resolution rate but also anticipate a higher response to the intervention which will balance (e.g. sample size calculation for a 25% spontaneous resolution rate in previously untreated non-recalcitrant warts but a higher 60% response rate to vitamin D would give a same sample size calculation of 60 with 30 subjects in each arm)

Endpoints

Primary:

Complete regression of index wart.

Secondary:

Partial regression of index wart as measured in percent surface area lost.

Complete or partial regression of up to 7 other warts followed.

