9.1	CONFIDENTIALITY	24
9.2	SOURCE DOCUMENTS	24
9.3	CASE REPORT FORMS	24
9.4	RECORDS RETENTION	25
10	STUDY MONITORING, AUDITING, AND INSPECTING	26
10.1	STUDY MONITORING PLAN	26
10.2	AUDITING AND INSPECTING	26
11	ETHICAL CONSIDERATIONS	26
12	STUDY FINANCES	26
12.1	FUNDING SOURCE	26
12.2	SUBJECT STIPENDS OR PAYMENTS	26
13	PUBLICATION PLAN	27
14	REFERENCES	27

LIST OF ABBREVIATIONS

AE	Adverse Event/Adverse Experience
CFR	Code of Federal Regulations
Co-I	Co-Investigator
CRF	Case Report Form
ECH	Employee and Community Health
ED	Emergency Department
HER	Electronic Health Record
EMR	Electronic Medical Record
FDA	Food and Drug Administration
GCP	Good Clinical Practice
HIPAA	Health Insurance Portability and Accountability Act
IND	Investigational New Drug Application
IRB	Institutional Review Board
IU	International Unit
Non-UPIRTSO	Non-Unanticipated Problem Involving Risk to Subjects or Others
PHI	Protected Health Information
PI	Principal Investigator
SAE	Serious Adverse Event/Serious Adverse Experience
UPIRTSO	Unanticipated Problem Involving Risk to Subjects or Others

Study Summary

Title	Efficacy of Intralesional Vitamin D injection for Treatment of Common Warts: A Randomized Controlled Trial
Running Title	Vitamin D injection for Treatment of Common Warts
Protocol Number	19-010219
Phase	Clinical study phase II
Methodology	Double blind; Randomized, placebo – controlled design
Overall Study Duration	The study will run until the n is reached with target based on sample size calculation.
Subject Participation Duration	Maximum of 168 days
Single or Multi-Site	Single
Objectives	In this study, we aim to explore the efficacy of intralesional vitamin D injection into cutaneous warts by comparing the rates of wart improvement and resolution between a population randomly selected to receive either blinded Vitamin D wart injections or placebo.
Number of Subjects	80 (40 intervention, 40 control)
Diagnosis and Main Inclusion Criteria	Adult ECH patients seen at the Mayo Clinic Rochester practices suffering from one or more cutaneous warts.. Both recalcitrant and non-recalcitrant warts will be included.
Study Product, Dose, Route, Regimen	Cholecalciferol (Vitamin D3), injection of 0.3 ml 40,000IU, intralesional (specifically at the base of the wart with needle centered under the wart) at baseline visit and weeks 4 and 8 as needed.
Duration of Administration	56 days
Reference therapy	Placebo

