7.2 Statistical Methods

Descriptive Statistics

There should be no significant temporal bias as season does not appear to affect wart refractoriness or resolution (though perhaps the increased vitamin D generated in skin in the summer would suggest a higher rate of spontaneous resolution if our hypothesis is correct). Secondary outcomes of partial resolution of warts based on visually and palpable size and photo-documented appearance will be recorded and reported as well. Fisher's exact test will be used to compare effects of placebo vs vitamin D3 injection on wart resolution.

Handling of Missing Data

Adherence to the protocol will be assessed by the study investigators through examination of data ensuring randomization and blinding, and self-reports of the study participants. Data from participants who for whatever reason deviate from the protocol will be handled by an intention to treat method in the final statistical analysis.

Primary Hypothesis: Vitamin D intralesional injection into cutaneous warts results in higher rates of complete resolution than saline placebo injection.

Fisher's exact test will be used to compare effects of placebo vs vitamin D3 injection on wart resolution.

Secondary Hypothesis

Partial regression of index wart as measured in percent surface area lost.

Multivariable linear regression will be used to assess the effect of vitamin D injection on final wart surface area, adjusting for initial surface area in the model.

Complete or partial regression of up to 7 other warts followed.

Fisher's exact test will be used to compare effects of placebo vs vitamin D3 injection on complete resolution of all additional warts. Multivariable linear regression will be used to assess the effect of vitamin D injection on final wart surface area of all additional warts, adjusting for initial surface area of the additional warts in the model.

Interim Analysis

The study dataset will be routinely monitored by the principle investigator and research coordinators to screen for any duplicate data entry and ensure sequential data input. Any adverse events or safety concerns will be immediately reported to the principle investigator and documented.

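### The plan states 80 subjects but calculates 60, and its claim that 25% vs 60% needs the same number as 5% vs 40% is wrong

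*Combined protocol and SAP*

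**What the plan says.** - **Stated number.** The Study Summary (Number of Subjects) and section 3.2 both give "80 (40 intervention, 40 control"). The Summary entry on overall duration adds: "The study will run until the n is reached with target based on sample size calculation".
- **Calculated number.** Section 7.1 takes 5% clearance on control and 35 points more on vitamin D, with alpha 0.05 and 80% power, and concludes: "we would need a sample size of 54 composed of 27 subjects receiving the intervention and 27 controls". It continues: "We will increase enrollment to 30 in each group to account for drop outs". That is 60 in total.
- **Second scenario.** If many enrolled warts are non-recalcitrant and non-plantar, section 7.1 expects a higher "spontaneous resolution rate but also anticipate a higher response to the intervention which will balance". Its example is 25% on control, where a "60% response rate to vitamin D would give a same sample size calculation of 60 with 30 subjects in each arm".
- **Test.** Section 7.2 states: "Fisher's exact test will be used to compare effects of placebo vs vitamin D3 injection on wart resolution". Neither 7.1 nor 7.2 says whether it is one- or two-sided. The primary hypothesis is directional: vitamin D "results in higher rates of complete resolution than saline placebo injection".
- **Drop-out.** Section 7.1 gives no rate.

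**The concern.** There are two faults. First, the stated enrolment and the calculated enrolment disagree by 20 subjects, and the Summary's rule for ending enrolment points to the calculation, which contradicts the Summary's own figure. A reader cannot tell whether stopping at 60 is completion or a shortfall.

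Second, section 7.1 treats an equal difference in proportions as an equal sample size. The variance of a proportion depends on its level, so moving both rates towards 50% raises the number needed. The sentence reassures the reader that a change in case mix costs nothing, and that is not so.

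The faults interact. The second scenario can occur, because section 4.1 admits non-recalcitrant warts and section 1.3 cites placebo or spontaneous clearance of 23% to 27% in earlier work. Which of the two targets applies decides whether that scenario reaches the plan's 80% power.

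**Working it through.** **Inputs.** From section 7.1: 5% vs 40%, 25% vs 60%, alpha 0.05, power 80%, 27 raised to 30 per arm. From section 7.2: Fisher's exact test. From the Summary and 3.2: 40 per arm. Assumed: a two-sided test (justified in step 3), and 10% loss, implied by 1 − 27/30.

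**1. Reproduce the plan's 27 per arm.** Use the pooled two-proportion formula with d = p2 − p1 and p̄ the mean of the two rates:

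n = [1.960·√(2p̄(1−p̄)) + 0.842·√(p1(1−p1) + p2(1−p2))]² / d²

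The continuity correction is n′ = (n/4)·[1 + √(1 + 4/(n·d))]².

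For 5/40:
- p̄ = 0.225, 2p̄(1−p̄) = 0.34875, and 0.05×0.95 + 0.40×0.60 = 0.2875.
- n = 21.13 and n′ = 26.53, so 27 per arm and 54 in total, as the plan states.

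**2. Apply the same formula to 25/60.**
- p̄ = 0.425, 2p̄(1−p̄) = 0.48875, and 0.25×0.75 + 0.60×0.40 = 0.4275.
- n = 30.11 and n′ = 35.59, so 36 per arm and 72 in total.
- The summed variance has risen by 0.4275/0.2875 = 1.49.

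**3. Is there a method under which the two scenarios need the same number?** Subjects per arm for 80% power:

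| Method | 5/40 | 25/60 | Gap |
|---|---|---|---|
| Two-sided pooled | 22 | 31 | 9 |
| Two-sided unpooled | 19 | 28 | 9 |
| Two-sided arcsine | 19 | 30 | 11 |
| Two-sided pooled, continuity-corrected | 27 | 36 | 9 |
| Two-sided unpooled, continuity-corrected | 24 | 33 | 9 |
| Two-sided exact chi-square, uncorrected | 20 | 30 | 10 |
| Two-sided exact Fisher | 24 | 37 | 13 |
| One-sided pooled | 17 | 24 | 7 |
| One-sided unpooled | 15 | 22 | 7 |
| One-sided arcsine | 15 | 24 | 9 |
| One-sided pooled, continuity-corrected | 22 | 30 | 8 |
| One-sided unpooled, continuity-corrected | 20 | 27 | 7 |
| One-sided exact Fisher | 20 | 30 | 10 |

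None of the 13 gives equal numbers; 25/60 always needs 7 to 13 more per arm. Only the two-sided pooled, continuity-corrected row gives 27 for 5/40. The one-sided rows give 15 to 22, which is why a two-sided test is inferred.

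**4. Power of Fisher's test at the two targets.** Exact enumeration over all 2×2 tables. The 27 and 36 columns are 30 and 40 less 10%.

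| Scenario and test | 27 | 30 | 36 | 40 |
|---|---|---|---|---|
| 5/40, two-sided | 84.0% | 89.3% | 95.2% | 97.3% |
| 25/60, two-sided | 64.9% | 71.9% | 79.7% | 86.2% |
| 25/60, one-sided | 78.0% | 80.6% | 90.2% | 90.9% |

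If the 10% lost are instead kept in the denominator as not cleared (25/60 becomes 22.5/54), two-sided power is 62.6% at 30 per arm and 78.1% at 40.

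**The case against.** The strongest reply is that this is a documentation mismatch and does not show an underpowered trial. Both places headed as the number of subjects say 80, and at 80 with no loss both scenarios exceed 80% power. The base case, on which 7.1 sizes the trial, is adequate at either target. A shortfall at 60 needs the target to be 60, the test to be two-sided, and the conditional second scenario to occur. All of that stands and limits the severity.

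The figure of 30 per arm for 25/60 is also defensible alone: two-sided arcsine (29.87), uncorrected chi-square and one-sided Fisher all give 30. That stands too. But those methods give 19, 20 and 20 for 5/40, not 27, so 7.1 cannot have used one method for both figures. It is also possible that the second 60 is a number before loss set beside a first 60 that includes it. Section 7.1 does not say, so a missing drop-out allowance is only an inference. On any of these readings the claim of balance fails.

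Sidedness matters most. One-sided, 60 subjects reach 80.6% for 25/60 with no loss, falling to 78.0% at 27 analysed. The two-sided inference rests on the sizing formula and not on any statement about the Fisher analysis, so the 71.9% must be read as conditional.

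**Conclusion.** The concern holds. Without any statistical assumption, the plan carries two enrolment targets, 80 and 60, and derives only the second. Also without assuming sidedness, the statement that the two scenarios balance to the same number is wrong, by 7 to 13 subjects per arm in every calculation tried and by 9 under the formula that reproduces the plan's own 27.

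The consequence is conditional. If Fisher's test is two-sided, 25/60 has 71.9% power at 60 enrolled (64.9% with 10% loss) and 86.2% at 80 (79.7% with 10% loss, marginally short of the stated 80%). The 5/40 scenario is not threatened at either target. This should be corrected, but the design itself need not change if 80 is the intended number.

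**What to change.** 1. Put one target in the Summary, section 3.2 and section 7.1.
2. In 7.1, delete the claims that the rates balance and that 25/60 yields an identical calculation.
3. State for both scenarios whether the test is one- or two-sided, one sizing method consistent with Fisher's test, the drop-out rate, and how drop-outs are counted in the primary analysis.
4. **If 80 is kept,** base 7.1 on it. For a two-sided test, report power of 97% (5/40) and 86% (25/60) at 40 per arm, and 95% and 79.7% at 36 analysed; if drop-outs count as not cleared, report 78.1% for 25/60. One possible derivation is 36/0.9 = 40 per arm, but the documents do not give it and the sponsor would have to confirm or replace it.
5. **If 60 is kept,** correct the Summary and 3.2, and disclose two-sided power of 72% for 25/60 (65% at 27 analysed).
6. If a one-sided test is chosen, use the one-sided figures instead.
7. Check stock against the chosen target. The 90 vials per arm in section 5.7 equal 30 subjects × 3 injections, but they do not settle which target applies: section 5.8 has stock prepared at intervals, and later injections depend on the wart persisting.

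The cost is wording, with no subjects beyond the 80 already stated. Keeping 60 means disclosing the lower power in the second scenario.

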7.2 Statistical Methods

Descriptive Statistics

There should be no significant temporal bias as season does not appear to affect wart refractoriness or resolution (though perhaps the increased vitamin D generated in skin in the summer would suggest a higher rate of spontaneous resolution if our hypothesis is correct). Secondary outcomes of partial resolution of warts based on visually and palpable size and photo-documented appearance will be recorded and reported as well. Fisher's exact test will be used to compare effects of placebo vs vitamin D3 injection on wart resolution.

Handling of Missing Data

Adherence to the protocol will be assessed by the study investigators through examination of data ensuring randomization and blinding, and self-reports of the study participants. Data from participants who for whatever reason deviate from the protocol will be handled by an intention to treat method in the final statistical analysis.

Primary Hypothesis: Vitamin D intralesional injection into cutaneous warts results in higher rates of complete resolution than saline placebo injection.

Fisher's exact test will be used to compare effects of placebo vs vitamin D3 injection on wart resolution.

Secondary Hypothesis

Partial regression of index wart as measured in percent surface area lost.

Multivariable linear regression will be used to assess the effect of vitamin D injection on final wart surface area, adjusting for initial surface area in the model.

Complete or partial regression of up to 7 other warts followed.

Fisher's exact test will be used to compare effects of placebo vs vitamin D3 injection on complete resolution of all additional warts. Multivariable linear regression will be used to assess the effect of vitamin D injection on final wart surface area of all additional warts, adjusting for initial surface area of the additional warts in the model.

Interim Analysis

The study dataset will be routinely monitored by the principle investigator and research coordinators to screen for any duplicate data entry and ensure sequential data input. Any adverse events or safety concerns will be immediately reported to the principle investigator and documented.

7.3 Subject Population(s) for Analysis

- All-treated population: Any subject randomized into the study that received at least one dose of study drug

8 Safety and Adverse Events

8.1 Definitions

Unanticipated Problems Involving Risk to Subjects or Others (UPIRTSO)

Any unanticipated problem or adverse event that meets the following three criteria:

- Serious: Serious problems or events that results in significant harm, (which may be physical, psychological, financial, social, economic, or legal) or increased risk for the subject or others (including individuals who are not research subjects). These include: (1) death; (2) life threatening adverse experience; (3) hospitalization - inpatient, new, or prolonged; (4) disability/incapacity - persistent or significant; (5) birth defect/anomaly; (6) breach of confidentiality and (7) other problems, events, or new information (i.e. publications, DSMB reports, interim findings, product labeling change) that in the opinion of the local investigator may adversely affect the rights, safety, or welfare of the subjects or others, or substantially compromise the research data, **AND**
- Unanticipated: (i.e. unexpected) problems or events are those that are not already described as potential risks in the protocol, consent document, not listed in the Investigator's Brochure, or not part of an underlying disease. A problem or event is "unanticipated" when it was unforeseeable at the time of its occurrence. A problem or event is "unanticipated" when it occurs at an increased frequency or at an increased severity than expected, **AND**
- Related: A problem or event is "related" if it is possibly related to the research procedures.

Adverse Event

An untoward or undesirable experience associated with the use of a medical product (i.e. drug, device, biologic) in a patient or research subject.

Serious Adverse Event

Adverse events are classified as serious or non-serious. Serious problems/events can be well defined and include;

- death
- life threatening adverse experience
- inpatient hospitalization or prolongation of existing hospitalization
- persistent or significant disability or incapacity
- substantial disruption of the ability to conduct normal life functions
- birth defect/congenital anomaly

and/or per protocol may be problems/events that in the opinion of the sponsor-investigator may have adversely affected the rights, safety, or welfare of the subjects or others, or substantially compromised the research data.

All adverse events that do not meet any of the criteria for serious, should be regarded as **non-serious adverse events**.

Adverse Event Reporting Period

For this study, the study treatment follow-up period is defined as 112 days following the last administration of study treatment.

Preexisting Condition

A preexisting condition is one that is present at the start of the study. A preexisting condition should be recorded as an adverse event if the frequency, intensity, or the character of the condition worsens during the study period.

General Physical Examination Findings

At screening, any clinically significant abnormality should be recorded as a preexisting condition. At the end of the study, any new clinically significant findings/abnormalities that meet the definition of an adverse event must also be recorded and documented as an adverse event.

Post-study Adverse Event

All unresolved adverse events should be followed by the sponsor-investigator until the events are resolved, the subject is lost to follow-up, or the adverse event is otherwise explained. At the last scheduled visit, the sponsor-investigator should instruct each subject to report, to the sponsor-investigator, any subsequent event(s) that the subject, or the subject's personal physician, believes might reasonably be related to participation in this study.

Abnormal Laboratory Values

There will be no routine clinical laboratory monitoring for the purpose of this study. However, if subjects present with signs or symptoms of vitamin D toxicity to a medical care provider, values for standard laboratory workup including 25(OH) vitamin D concentration, calcium, phosphorus, creatinine would be monitored as well as any follow-up labs within the study's follow-up period.

A clinical laboratory abnormality will be documented as an adverse event if any of these values are found to be above normal ranges.

Hospitalization, Prolonged Hospitalization or Surgery

Any adverse event that results in hospitalization or prolonged hospitalization should be documented and reported as a serious adverse event unless specifically instructed otherwise in this protocol. Any condition responsible for surgery should be documented as an adverse event if the condition meets the criteria for an adverse event.

Neither the condition, hospitalization, prolonged hospitalization, nor surgery are reported as an adverse event in the following circumstances:

- Hospitalization for diagnostic or elective surgical procedures for a preexisting condition.

